5. VARIABLES AND THEIR ASSESSMENT

5.1 TRIAL ENDPOINTS

All endpoints listed below apply for both parts of the trial.

5.1.1 Primary Endpoint(s)

The primary endpoint to assess safety and tolerability of BI 443651, is the frequency (in percent) of subjects with treatment-emergent adverse events (TEAE) over the treatment period. The primary endpoint will be reported separately for Healthy volunteers and CF subjects.

5.1.2 Secondary Endpoint(s)

The following pharmacokinetic parameters will be determined if feasible for healthy volunteers in Part 1

After the first dose on Day 1:

- C_{\max} (maximum measured concentration of the analyte in plasma)
- AUC_{0-12} (area under the concentration-time curve of the analyte in plasma until 12 h after the first dose)

After the last dose on Day 7 (:

- $C_{\max,ss}$ (maximum measured concentration of the analyte in plasma at steady state over a uniform dosing interval τ)
- $AUC_{\tau,ss}$ (area under the concentration-time curve of the analyte in plasma at steady state over a uniform dosing interval τ)

5.1.3 Further Endpoint(s)

Further safety criteria of interest:

- Related AEs (including clinically relevant findings from the physical examination)
- Safety laboratory tests
- 12-lead ECG
- Vital signs (blood pressure, pulse rate)
- Pulmonary function tests (FEV₁, FVC, FEF₂₅₋₇₅)

5.3 ASSESSMENT OF SAFETY

5.3.1 Physical examination

A physical examination will be carried out according to the [Flows Chart I](#) & [Flow Chart II](#) and will be performed as complete physical examination; at screening and end of study (e.o.s.) visits. In addition further physical examination should be performed if clarification of an AE is necessary.

All clinically significant findings at screening will be documented on the source documents and recorded in the eCRF as baseline conditions.

After randomization, new clinically significant findings or worsening of screening conditions that are, in the opinion of the investigator, clinically significant or meet other adverse event criteria defined in [Section 5.3.9](#) will be reported as adverse events.

Body weight and height will be determined at the screening visit (Visit 1) as per [Flow Chart I](#) & [Flow Chart II](#). In addition body weight will be determined at end of study (e.o.s.) visit. Body weight and height will be documented on the source documents and recorded. Body height will be recorded in the spirometry measurement device and the body weight of the screening Visit 1 (relevant for body plethysmography assessment in CF subjects) will be recorded in the body plethysmography device and used for subsequent measurements.

5.3.2 Vital Signs

Systolic and diastolic blood pressures (BP) as well as pulse rate (PR) will be measured by a blood pressure monitor at the times indicated in [Flow Chart I](#) & [Flow Chart II](#) after subjects have rested for at least 5 min in a supine position (if blood sampling for PK/safety purposes will be drawn from a cannula, this procedure will not affect the resting time). Where possible, all recordings should be made using the same blood pressure recording instrument on the same arm.

5.3.3 Medical examinations

At the screening visit, the medical examination will include documentation of subject information, informed consent, demographics including height and body weight, smoking and alcohol history, relevant medical history and concomitant therapy, review of inclusion and exclusion criteria, review of vital signs (BP, PR), 12-lead ECG, laboratory tests, and a physical examination. At the end of trial examination, it will include review of vital signs, 12-lead ECG, laboratory tests, and a physical examination.

5.3.4 Spirometry

Spirometry will be performed according to ATS/ERS guidelines for pulmonary function testing [[P05-12782](#)] in order to characterise the study population, to monitor individuals safety in regard to CF and as an exploratory assessment of drug effect. The CF subjects must qualify by demonstrating a pre-bronchodilator clinic measured $FEV_1 \geq 70\%$ of predicted normal (calculated according to GLI [[R15-0845](#)]) measured ≥ 8 hours after the last use of short acting bronchodilator at Visit 1 and prior to randomisation.

PFTs will be performed in triplicate using spirometry equipment provided by the site and calibrated by study staff on all test days. Equipment and techniques should conform to American Thoracic Society (ATS) criteria [[P05-12782](#)]. An ambulatory spirometer, Asthma Monitoring Device (AM3®), will be used to perform PFTs while the subject is at home (ex-clinic).

Spirometry in-clinic will be conducted with the subject in a seated position. Spirometry using the AM3® device will be conducted in a standing position. It is preferable that the same trained individual performs the PFTs for a given subject. The best of three efforts will be defined as the highest FEV_1 and the highest FVC each obtained on any of three blows meeting the ATS criteria (with a maximum of eight attempts). FEV_1 , FVC, FEF_{25-75} and PEF will be measured as indicated in [Flow Chart I](#) & [Flow Chart II](#) and recorded in the eCRF. Ex-clinic measured values of PEF will not need to be collected in the database. The best of the

three pre-dose FEV₁ measurements will be defined as trough FEV₁. The 24-hour clock time of the first manoeuvre for each PFT time point will be recorded.

5.3.5 Body Plethysmography

Airway resistance (Raw) will be measured with a constant volume whole-body plethysmograph as supplied and calibrated by the trial site. Measurements will be taken with the subject in the sitting position and carried out by an observer. The mean of at least three values recorded, will be taken as airway resistance. Refer to [Flow Chart I](#) for time points. Practice sessions can be performed with volunteers from consent and screening onwards for those volunteers that would like to experience the body plethysmography prior to collecting data. This data will not be captured or collected.

5.3.6 CF control during the trial

The safety of the subjects regarding CF during the trial will be assured by monitoring of FEV₁ and assessment of rescue and controller medication use and CF signs and symptoms. Subjects should be discontinued from the trial if, in the opinion of the Principle investigator, the subject is developing unstable CF, based on assessment of safety parameters described above.

The subjects will be instructed to make themselves available for the regular telephone monitoring for drug administration and their general well-being. Site staff will assess drug compliance, a subject's general well-being, rescue medication use and FEV₁ measurements via in-clinic visits, documented telephone monitoring and the AM3® device.

At home (ex-clinic) FEV₁ measurements:

At Day 1 for CF subjects, eligible subjects will receive hand-held electronic spirometers, [AM3®, eResearch Technology, Inc] from the site for their regular use during the entire study to monitor their FEV₁ whilst at home ([Flow Chart II](#)). In addition, CF subjects will perform an unsupervised manoeuvre on their AM3® device at screening (Day -7 to -3). The subject should perform three FEV₁ manoeuvres consistently, in a standing position with the AM3®. Instructions for use of the AM3® device will be provided to the subject.

All acceptable FEV₁ values are stored in the AM3® device with date and time of recording.

CF subjects:

Whilst the subject is at home (ex-clinic) morning and evening FEV₁ measurements will be performed on the AM3® prior to administration of study medication and background respiratory medication. In the morning, whilst the subject is at home (ex-clinic), the manoeuvre will be performed prior to or as part of the telephone visit under the supervision of the study site staff. If a relevant drop in FEV₁ compared to baseline (Day -7 to Day -3, morning, unsupervised AM3® manoeuvre) is observed the site staff will evaluate whether the subject needs to return to clinic prior to the morning visit.

During in clinic visits the AM3® data will be downloaded to a computer, the corresponding report printed and the data reviewed by the site in the morning on each visit day. The investigator will review/discuss the data with the subject and assesses the subject in regard to the data observed.

FEV₁ should also be measured at any time whenever the subject feels breathless or otherwise uncomfortable. The AM3® is primed to alarm following a 20% relative drop vs. baseline in

FEV₁. Subjects must not take their trial medication dose, and must call the site if the device alarms.

FEV₁ data will be downloaded to a computer at each visit and printed out for review, signature and date by the investigator. Equipment will be withdrawn at end of study. Print-outs will be filed in the ISF.

Telephone visits:

During the treatment period when subjects are at home (ex-clinic), regular appointments for telephone calls between subject and investigator will be made. Calls will be made in the morning and evening for CF subjects. The following issues will be covered at each telephone visits in a sequential way:

1. Subjects will be reminded to take their correct trial medication dose.
2. Subjects will be questioned regarding general wellbeing.
3. Whether the subjects have performed a FEV₁ measurement with the AM3® that evening or that morning, if not subjects will need to perform the measurements during the course of the telephone calls. Site staff will ask whether the AM3 device has alarmed.
4. Subjects will be asked whether any AEs have occurred
5. Subjects will be reminded to conduct a FEV₁ reading and subsequently administer drug in the following evening or morning.

In any case of emergency during the trial the investigator must be available by phone for immediate assistance, therefore the subjects will be provided with 24-hour contact details.

Note: Documentation of AE if any (also if related due to i.e. a worsening of AE), change of any medication and intake of study medication have to be captured in the medical records and eCRF.

Details of any telephone visits as mentioned above, will be documented as source data in the subjects medical records.

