- 13) Unsupervised Pulmonary Function (FEV₁, PEF) with AM3® device
- 14) Phone call to be made twice a day, ideally at the time of study drug administration ([see section 5.3.6](#)). During the afternoon or evening calls, AEs should be collected in line with a morning call
- 15) Allocation to treatment may be performed at any time following enrolment but must be completed prior to first drug administration. Randomisation not required for CF subjects undergoing second treatment period
- 16) AEs and concomitant therapies will be recorded throughout the trial, but will be specifically asked for at the time points indicated in the [Flow Chart II](#) above including during phone calls when patients are ex clinic.
- 17) Respimat device and AM3® device training initially, then instruction (if required).
- 18) Systolic and diastolic blood pressures (BP) as well as pulse rate (PR) will be measured by a blood pressure monitor at the times indicated in the Flow Chart II, after subjects have rested for at least 5 min in a supine position.
- 19) Includes, urine pregnancy test for females at Screening, Day 1, Day 7, Day 14 and Day 30. Serum pregnancy test at Day -5 to -3, and e.o.s. visit.
- 20) To be measured on home based spirometer (AM3®), prior to drug administration.
- 21) Baseline ECG (Day 1) must be in triplicate. All other ECGs to be single.
- 22) Urine drug screen and alcohol breath test to be performed at both screening and Pre-dose Day 1.,
- 24) Serum electrolytes to be collected using local laboratory values in addition to central laboratory values.
- 25) Planned time is required for technical reasons and the actual dates and times could be between Day -7 to -3.

TABLE OF CONTENTS

| | |
|---|-----------|
| CLINICAL TRIAL PROTOCOL..... | 1 |
| TITLE PAGE | 1 |
| CLINICAL TRIAL PROTOCOL SYNOPSIS | 2 |
| FLOW CHART I – HEALTHY VOLUNTEERS | 5 |
| FLOW CHART II – CF SUBJECTS..... | 8 |
| TABLE OF CONTENTS | 11 |
| ABBREVIATIONS..... | 15 |
| 1. INTRODUCTION..... | 17 |
| 1.1 MEDICAL BACKGROUND | 17 |
| 1.2 DRUG PROFILE | 18 |
| 1.2.1 Nonclinical pharmacology..... | 18 |
| 1.2.2 Safety pharmacology..... | 19 |
| 1.2.3 Toxicology | 19 |
| 1.2.5 Drug product | 20 |
| 1.2.6 Clinical studies and experience in humans | 20 |
| 2. RATIONALE, OBJECTIVES, AND BENEFIT - RISK ASSESSMENT | 22 |
| 2.1 RATIONALE FOR PERFORMING THE TRIAL | 22 |
| 2.2 TRIAL OBJECTIVES..... | 22 |
| 2.3 BENEFIT - RISK ASSESSMENT..... | 22 |
| 2.3.1 Procedure-related risks | 23 |

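### The home-call checklist for CF subjects prompts the dose before it checks FEV1 and the AM3 alarm, against the protocol's own FEV1-first rule

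*Protocol*

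**What the plan says.** Section 5.3.6 introduces the telephone visits with an explicit order: "The following issues will be covered at each telephone visits in a sequential way". The five items, in that order, are:

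1. a dose reminder: "Subjects will be reminded to take their correct trial medication dose";
2. general wellbeing;
3. whether FEV1 has been measured on the AM3 that morning or evening, "if not subjects will need to perform the measurements during the course of the telephone calls", followed by whether the AM3 has alarmed;
4. adverse events;
5. a reminder for the next session to take an FEV1 "reading and subsequently administer drug in the following evening or morning".

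The same section sets the rules that these calls support. Home FEV1 is to be measured morning and evening "prior to administration of study medication and background respiratory medication", and Flow Chart II footnote 20 repeats this. The AM3 alarms on a 20% relative fall from baseline, and then: "Subjects must not take their trial medication dose, and must call the site if the device alarms". For the morning, "the manoeuvre will be performed prior to or as part of the telephone visit under the supervision of the study site staff". Flow Chart II footnote 14 sets the timing of calls: "Phone call to be made twice a day, ideally at the time of study drug administration". Section 4.3 makes the morning and evening call the occasion on which subjects are reminded to dose.

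**The concern.** The prescribed order runs against the rule that the call should help enforce. The prompt to dose comes first and carries no condition; the check that could stop the dose comes two items later. Wellbeing and adverse events also follow the prompt, so no safety question of any kind precedes it.

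At stake is the pre-dose stop for a fall in lung function. Section 2.3.2 lists home AM3 monitoring among the safety measures. There is a reason to want it to work: Section 1.2.1 reports that the drug enhanced acetylcholine-induced bronchoconstriction in guinea pigs by 51% and 117% at the two doses tested. Section 2.3.2 judges this not relevant to CF patients but states that respiratory function will be monitored. Section 3.3.3 allows CF subjects with stable concomitant asthma to enrol.

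**Working it through.** The plan has no figure to reproduce on this point. The check is a reading of the steps, plus a count of how often they apply.

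**Order of steps, when FEV1 has not been done before the call**

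| Step | What 5.3.6 and footnote 20 require | What the call order produces |
|---|---|---|
| First | FEV1 measured | Reminder to dose (item 1) |
| Next | Alarm or no alarm on a 20% fall | Wellbeing (item 2) |
| Then | Dose if no alarm; no dose and a call to the site if alarm | FEV1 measured, alarm question (item 3) |

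**Is that case foreseen?** Yes. The morning manoeuvre may be part of the call, and item 3 provides for a late measurement at either call. Calls are ideally made at dosing time, so the reminder may reach the subject just when the dose is due.

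**Does the alarm rule cover that dose?** No. Until the subject blows, the device has no reading for this dose and cannot have alarmed on it. The only protection left at item 1 is the general rule that FEV1 precedes the dose, which item 1 does not mention.

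**Does item 5 repair it?** In part. It gives the right order, but for the following session.

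**How often the checklist is used** (nominal days, ignoring the Day 7 and Day 14 windows; Sections 4.1.4 and 5.3.6, Flow Chart II):

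- Doses per period: 13 × 2 + 1 = 27.
- Supervised in clinic (mornings of Days 1, 7 and 14): 3. Home doses: 27 − 3 = 24.
- Full home days: Days 2–6 and 8–13, so 5 + 6 = 11. Calls at two a day: 11 × 2 = 22 per period.
- Over two periods: 22 × 2 = 44 calls per subject, of which 11 × 2 = 22 are morning calls.
- The remaining 24 − 22 = 2 home doses per period are the Day 1 and Day 7 evenings, not counted here.

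The documents give no rate for FEV1 being left until the call, for dosing on the reminder, or for a 20% fall, so no expected number of affected doses can be calculated.

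**The case against.** The strongest reply is that the governing rule is already correct and stated twice. FEV1 before the dose does not depend on an alarm, so a subject with no reading may not dose yet, whatever the order of topics. Item 1 does not tell the subject to inhale at once. Item 5 is given at every call, so from the second call of each run of home days the subject has just been told the right order for the dose now due. Device training comes earlier still.

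Harm also needs several things together: no FEV1 before the call, inhalation between items 1 and 3 while site staff are on the line, and a fall of at least 20%. Even then the fall is found minutes later in the same call. The dose is 600 µg, CF dosing starts only after 1200 µg b.i.d. has been well tolerated in healthy volunteers, and rescue medication and 24-hour contact are in place.

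All of this stands as a limit on the size of the problem. It does not justify the order. Staff working through a list that must be taken in sequence will give the dose prompt first, and correct conduct then rests on the subject remembering a rule that the prompt leaves out. Item 3 itself expects that some subjects will not have measured FEV1 by then. The documents give no reason for the present order.

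**Conclusion.** The point holds: the stated call sequence is inconsistent with the FEV1-before-dose rule and can prompt a dose before a 20% fall is detected. It is an inconsistency in ordering and not a missing safeguard, of modest importance, and should be corrected.

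This rests on two readings: that the sequence is meant literally, as the section says, and that some subjects will reach the call without a reading, as the section provides for. How often a dose would be affected is unknown. Any effect on the home spirometry summaries is likely small, because AM3 readings are stored with date and time and those analyses are descriptive. The primary endpoint definition is not touched.

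**What to change.** Reorder the list in Section 5.3.6 and make the reminder conditional:

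1. General wellbeing.
2. FEV1 measured this morning or evening, or measured now; has the FEV1-drop alarm sounded?
3. Adverse events.
4. If FEV1 has been measured and that alarm has not sounded, remind the subject to take the dose. If it has sounded, the dose is withheld and the site evaluates whether the subject must return to clinic.
5. The existing reminder for the next FEV1 reading and dose.

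The question in item 2 should name the FEV1-drop alarm, because Section 4.3 says that the AM3 also alarms as a reminder to take the drug, so asking only whether the device has alarmed is ambiguous.

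The cost is reordering one list and rewording its FEV1/alarm and dose-reminder items. No procedure, visit or data item is added.

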5.3.7 Safety laboratory parameters

For the assessment of laboratory parameters, blood and urine samples will be collected by the trial site at the time points indicated in [Flow Chart I](#) & [Flow Chart II](#).

If safety laboratory measurement is performed with other blood collection, e.g. PK sampling, safety laboratory measurement will always be performed first, preferably without any tourniquet.

The parameters that will be determined are listed in [Tables 5.3.7: 1](#) and [5.3.7: 2](#). Reference ranges will be provided in the ISF

Manual differential white blood cell count or urine sediment examinations will only be performed if there is an abnormality in the automatic blood cell count or in the urinalysis, respectively.

Table 5.3.7: 1

Routine laboratory tests

| Category | Test name | A¹ | B² | C³ |
|---|--|----------------------|----------------------|----------------------|
| Haematology | Haematocrit | X | X | X |
| | Haemoglobin | X | X | X |
| | Red blood cells (RBC) | X | X | X |
| | White blood cells (WBC) | X | X | X |
| | Platelets | X | X | X |
| | Reticulocyte count | X | X | X |
| Automatic WBC differential (relative and absolute) | Neutrophiles | X | X | X |
| | Eosinophils | X | X | X |
| | Basophils | X | X | X |
| | Monocytes | X | X | X |
| | Lymphocytes | X | X | X |
| Manual differential WBC (if automatic differential WBC is abnormal) | Polymorphnuclear neutrophils (segs), band (only for HV) neutrophils (stabs), eosinophils, basophils, monocytes, lymphocytes | | | |
| Coagulation | Activated partial thromboplastin time (aPTT) | X | X | X |
| | Prothrombin Time (Quick and INR) | X | X | X |
| Enzymes | Aspartate aminotransferase (AST/GOT, SGOT) | X | X | X |
| | Alanine aminotransferase (ALT/GPT, SGPT) | X | X | X |
| | Alkaline phosphatase | X | X | X |
| | Gammaglutamyl transferase (GGT) | X | X | X |
| | Lactate dehydrogenase | X | X | X |
| | Amylase | X | X | X |
| | Lipase | X | X | X |

Table 5.3.7: 1

Routine laboratory tests (cont.)

| Category | Test name | A¹ | B² | C³ |
|---|---|----------------------|----------------------|----------------------|
| Substrates | Glucose (plasma) | X | - | - |
| | Creatinine | X | X | X |
| | eGFR, calculated from serum creatinine using CKD-EPI formula | X | X | X |
| | Bilirubin, total | - | - | - |
| | Bilirubin, direct | X | X | X |
| | Cholesterol, total | X | X | X |
| | Triglycerides | X | X | X |
| | C-reactive protein | X | X | X |
| | Urea | X | X | X |
| Electrolytes | Calcium | X | X | X |
| | Sodium | X | X | X |
| | Potassium | X | X | X |
| | Chloride | X | X | X |
| Hormones | Thyroid stimulating hormone (TSH) | X | - | - |
| | Progesterone | X | ** | - |
| Urinalysis (Stix) [Urin-Sediment will be performed, if urinalysis abnormal] | Urine nitrite | X | - | X |
| | Urine protein | X | - | X |
| | Urine glucose | X | - | X |
| | Urine ketone | X | - | X |
| | Urobilinogen | X | - | X |
| | Urine bilirubin | X | - | X |
| | Urine RBC | X | - | X |
| | Urine WBC | X | - | X |
| | Urine pH | X | - | X |
| * From urine collection at 0-4, 4-8 and 8-12 hr | Urine potassium | - | X | - |
| | Urine sodium | - | X | - |
| | Urine chloride | - | X | - |
| | Urine creatinine | - | X | - |
| | Potassium-creatinine-quotient | - | X | - |
| | Sodium-creatinine-quotient | - | X | - |
| Urine sediment (microscopic examination if erythrocytes, leukocytes nitrite or protein are abnormal in urine) | Only positive findings will be reported (for instance, the presence of sediment bacteria, casts in sediment, squamous epithelial cells, erythrocytes, leukocytes) | | | |

¹A: parameters to be determined at screening examination

²B: parameters to be determined during the study (for time points refer to [Flow Chart I](#) & [Flow Chart II](#))

³C: parameters to be determined during the Follow-up-examination

* Urine collected and samples taken from 0-12h will be stored at room temperature. Only to be collected on PK profile days for HV.

** Progesterone will need to be taken prior to second treatment period, for WOCBP.

The tests listed in [Table 5.3.7: 2](#) are exclusionary laboratory tests which may be repeated as required. The results will not be entered in the CRF/database and will not be reported in the CTR. It is planned to perform these tests during screening only. Drug screening will be performed at screening and on Day 1.

Table 5.3.7: 2

Exclusionary laboratory tests

| Functional lab group | Test name |
|-----------------------------|---|
| Drug screening (urine) | Amphetamine/MDA Barbiturates Benzodiazepine Cannabis Cocaine Methadone Methamphetamines/MDMA/XTC Opiates Phencyclidine Tricyclic antidepressants |
| Infectious serology (blood) | Hepatitis B surface antigen (qualitative) Hepatitis B core antibody (qualitative) Hepatitis C antibodies (qualitative) HIV-1 and HIV-2 antibody (qualitative) |

The laboratory tests listed in [Table 5.3.7: 1](#) and 5.3.7: 2 will be performed by the central laboratory, with the exception of the urine pregnancy tests (administered using a urine dipstick), urine drug abuse and alcohol breath tests.

With regards to serum electrolytes samples, where local laboratory results are also used, central laboratory results will take precedence in the interpretation of the results. Local laboratory results will be stored as source data at the trial site and will take precedence for initial and continued dosing decisions (e.g. K⁺). Local laboratory values will not be entered into the database.

Laboratory data will be transmitted electronically from the central laboratory to the trial site.

5.3.8 *Electrocardiogram*

Standard 10 second twelve-lead resting ECGs (I, II, III, aVR, aVL, aVF, V1 - V6) will be recorded using a computerised electrocardiograph (MAC 2000, GE Medical Systems, Freiburg, Germany) at the time points given in [Flow Chart I](#) & [Flow Chart II](#). Electrode placement will be performed according to the method of Wilson, Goldberger and Einthoven modified by Mason and Likar (hips and shoulders instead of ankles and wrists). Precise electrode placement will be marked with an indelible mark on the skin to allow reproducible placement throughout the study.

In order to achieve a stable heart rate at rest and to assure high quality recordings at comparable resting phases, all ECGs will be recorded for a 10-sec duration after the subjects have rested for at least 5 min in a supine position (if blood sampling for PK/safety purposes will be drawn from a cannula, this procedure will not affect the resting time). The site personnel will be instructed to assure a relaxed and quiet environment so that all subjects are at complete rest during the recordings. ECG assessment will always precede all other study procedures of the same time point to avoid impact of sampling on the ECG quality.

Triple ECGs (three ECGs recorded within 180 sec) will be recorded as the baseline on Day 1, before the first drug administration for all volunteer and subject groups. A second baseline

will be performed on Day 1 of Treatment Period 2 for CF subjects. For the healthy volunteers group all ECGs on Day 1, 2, 7 and 8, will be recorded in triplicate. For all other subject groups, single ECGs will be recorded, except for baseline (Day 1).

ECGs may be repeated for quality reasons (like alternating current artefacts, muscle movements, electrode dislocation).

All ECGs that are locally printed will be evaluated by the investigator or a designee. For triplicate ECG QTcF values, the mean value will be calculated and interpreted by the investigator or designee. Additional (unscheduled) ECGs may be collected by the investigator for safety reasons. These ECGs are assigned to the prior scheduled time point. Unscheduled ECGs will not be included into the statistical analysis of interval lengths and not evaluated centrally.

For the inclusion or exclusion ([see Section 3.3](#)) of a subject and for the assessment of cardiac safety during the study, the QT and QTcF values generated by the ECG machines or their manual corrections by the investigators will be used. In doubtful cases, ECGs may be sent upfront for centralised evaluation (see below). In this case, these centrally measured results would overrule any other results obtained.

Abnormal findings will be reported as AEs (during the trial) or baseline conditions (at screening) if judged clinically relevant by the investigator. Any ECG abnormalities will be monitored carefully and, if necessary, the subject will be removed from the trial and will receive the appropriate medical treatment. For all volunteers and subjects, for determination of safety and continued inclusion in the study the mean ECG of triplicates will be used for the evaluation.

All ECGs will be stored electronically and transmitted to an ECG core lab
). At minimum, electrocardiograms recorded at the following time points will be evaluated centralized at the core lab:

- Healthy volunteers: Days 1 and 2, and Days 7 and 8 (triplicate ECGs, only)
- CF subjects: All ECGs

The analysis will include the determination of the intervals RR, PR, QRS and QT measured semi-automatically. Other parameters (e.g. cardiac axis) are determined by a validated GE 12-SL-algorithm or equivalent but do not undergo semi-automatic evaluation. All interval measurements in one subject will be performed on the same lead. The intervals will be measured from four cardiac cycles (beats) in lead II. If lead II shows a flat T wave or is not measurable for any reason, lead V5 will be used, or if that lead is not measurable, then lead I will be used. The lead actually used will be reported in the CTR. HR and QTc (QT interval corrected for HR, e.g. QTcF and QTcB) will be determined in-house (see TSAP for details).

For CF subjects, morphological analyses of the centrally evaluated ECGs (see above) will be performed by a board-certified cardiologist or equivalent. In case of triplicate ECGs recorded at a time point one ECG will be selected randomly for this evaluation. In case additional (unscheduled) ECGs due to safety reasons are recorded at the study site, these ECGs are assigned to the previous scheduled time point, and all ECGs of this time point including the additional ECGs will undergo interpretation. The ECG interpretation will include an overall assessment and a classification of each finding (normal, abnormal clinically relevant, abnormal clinically not relevant, not assessable), in regard to rhythm, conduction and morphological abnormalities, presence of myocardial infarction, ST segment deviations, T-wave morphology (normal, flat, inverted or biphasic) and presence of U-wave (normal and

Proprietary confidential information © 2017 Boehringer Ingelheim International GmbH or one or more of its affiliated companies

abnormal). Abnormalities detected during centralised ECG evaluation will not necessarily qualify as AE.

For blinding arrangements see [section 4.1.5](#).

For quality assurance and control of the measurements, all ECGs of a subject will be subsequently reviewed by the ECG technician supervisor or his/her designee with respect to the overall variance of the measured intervals, in order to detect accidentally switching of leads and/or false subject assignments of the ECGs. After the quality control the fiducial point markings will be reviewed by the cardiologist assigned to the study.

Assessed ECGs will comply with the ICH E14 guidance document and supplements [[R05-2311](#), [R13-0801](#), [R13-4095](#)] as well as the FDA requirements for annotated digital ECGs [[R09-4830](#)].

